8.3. Severity Assessment

If required on the AE page of the CRF, the investigator will use the adjectives MILD, MODERATE, or SEVERE to describe the maximum intensity of the AE. For purposes of consistency, these intensity grades are defined as follows:	
MILD	Does not interfere with subject's usual function.
MODERATE	Interferes to some extent with subject's usual function.
SEVERE	Interferes significantly with subject's usual function.

Note the distinction between the severity and the seriousness of an AE. A severe event is not necessarily an SAE. For example, a headache may be severe (interferes significantly with the subject's usual function) but would not be classified as serious unless it met one of the criteria for SAEs, listed above.

8.4. Special Situations

8.4.1. Protocol-Specified Serious Adverse Events

There are no protocol-specified SAEs in this study. All SAEs will be reported to Pfizer Safety by the investigator as described in previous sections, and will be handled as SAEs in the safety database.

8.4.2. Potential Cases of Drug-Induced Liver Injury

Humans exposed to a drug who show no sign of liver injury (as determined by elevations in transaminases) are termed “tolerators,” while those who show transient liver injury, but adapt are termed “adaptors.” In some subjects, transaminase elevations are a harbinger of a more serious potential outcome. These subjects fail to adapt and therefore are “susceptible” to progressive and serious liver injury, commonly referred to as drug-induced liver injury (DILI). Subjects who experience a transaminase elevation above 3 times the upper limit of normal (\times ULN) should be monitored more frequently to determine if they are an “adaptor” or are “susceptible.”

In the majority of DILI cases, elevations in aspartate aminotransferase (AST) and/or alanine aminotransferase (ALT) precede total bilirubin (TBili) elevations ($>2 \times$ ULN) by several days or weeks. The increase in TBili typically occurs while AST/ALT is/are still elevated above $3 \times$ ULN (ie, AST/ALT and TBili values will be elevated within the same lab sample). In rare instances, by the time TBili elevations are detected, AST/ALT values might have decreased. This occurrence is still regarded as a potential DILI. Therefore, abnormal elevations in either AST OR ALT in addition to TBili that meet the criteria outlined below are considered potential DILI (assessed per Hy’s law criteria) cases and should always be considered important medical events, even before all other possible causes of liver injury have been excluded.

The threshold of laboratory abnormalities for a potential DILI case depends on the subject’s individual baseline values and underlying conditions. Subjects who present with the following laboratory abnormalities should be evaluated further as potential DILI (Hy’s law) cases to definitively determine the etiology of the abnormal laboratory values:

- Subjects with AST/ALT and TBili baseline values within the normal range who subsequently present with AST OR ALT values $>3 \times$ ULN AND a TBili value $>2 \times$ ULN with no evidence of hemolysis and an alkaline phosphatase value $<2 \times$ ULN or not available.
- For subjects with baseline AST **OR** ALT **OR** TBili values above the ULN, the following threshold values are used in the definition mentioned above, as needed, depending on which values are above the ULN at baseline:

- Preexisting AST or ALT baseline values above the normal range: AST or ALT values >2 times the baseline values AND $>3 \times \text{ULN}$; or $>8 \times \text{ULN}$ (whichever is smaller).
- Preexisting values of TBili above the normal range: TBili level increased from baseline value by an amount of at least $1 \times \text{ULN}$ or if the value reaches $>3 \times \text{ULN}$ (whichever is smaller).

Rises in AST/ALT and TBili separated by more than a few weeks should be assessed individually based on clinical judgment; any case where uncertainty remains as to whether it represents a potential Hy's law case should be reviewed with the sponsor.

The subject should return to the investigator site and be evaluated as soon as possible, preferably within 48 hours from awareness of the abnormal results. This evaluation should include laboratory tests, detailed history, and physical assessment.

In addition to repeating measurements of AST and ALT and TBili, laboratory tests should include albumin, creatine kinase (CK), direct and indirect bilirubin, gamma-glutamyl transferase (GGT), prothrombin time (PT)/international normalized ratio (INR), total bile acids, alkaline phosphatase and acetaminophen drug and/or protein adduct levels. Consideration should also be given to drawing a separate tube of clotted blood and an anticoagulated tube of blood for further testing, as needed, for further contemporaneous analyses at the time of the recognized initial abnormalities to determine etiology. A detailed history, including relevant information, such as review of ethanol, acetaminophen (either by itself or as a coformulated product in prescription or over-the-counter medications), recreational drug, supplement (herbal) use and consumption, family history, sexual history, travel history, history of contact with a jaundiced person, surgery, blood transfusion, history of liver or allergic disease, and potential occupational exposure to chemicals, should be collected. Further testing for acute hepatitis A, B, C, D, and E infection and liver imaging (eg, biliary tract) may be warranted.

All cases demonstrated on repeat testing as meeting the laboratory criteria of AST/ALT and TBili elevation defined above should be considered potential DILI (Hy's law) cases if no other reason for the liver function test (LFT) abnormalities has yet been found. **Such potential DILI (Hy's law) cases are to be reported as SAEs, irrespective of availability of all the results of the investigations performed to determine etiology of the LFT abnormalities.**

A potential DILI (Hy's law) case becomes a confirmed case only after all results of reasonable investigations have been received and have excluded an alternative etiology.

8.4.3. Exposure to the Investigational Product During Pregnancy or Breastfeeding, and Occupational Exposure

Exposure to the investigational product under study during pregnancy or breastfeeding and occupational exposure are reportable to Pfizer Safety within 24 hours of investigator awareness.

8.4.3.1. Exposure During Pregnancy

For both unapproved/unlicensed products and for marketed products, an exposure during pregnancy (EDP) occurs if:

- A female becomes, or is found to be, pregnant either while receiving or having been exposed (eg, because of treatment or environmental exposure) to the investigational product; or the female becomes or is found to be pregnant after discontinuing and/or being exposed to the investigational product;
- An example of environmental exposure would be a case involving direct contact with a Pfizer product in a pregnant woman (eg, a nurse reports that she is pregnant and has been exposed to chemotherapeutic products).
- A male has been exposed (eg, because of treatment or environmental exposure) to the investigational product prior to or around the time of conception and/or is exposed during his partner's pregnancy.

If a subject or subject's partner becomes or is found to be pregnant during the subject's treatment with the investigational product, the investigator must report this information to Pfizer Safety on the CT SAE Report Form and an EDP supplemental form, regardless of whether an SAE has occurred. In addition, the investigator must submit information regarding environmental exposure to a Pfizer product in a pregnant woman (eg, a subject reports that she is pregnant and has been exposed to a cytotoxic product by inhalation or spillage) to Pfizer Safety using the EDP supplemental form. This must be done irrespective of whether an AE has occurred and within 24 hours of awareness of the exposure. The information submitted should include the anticipated date of delivery (see below for information related to termination of pregnancy).

Follow-up is conducted to obtain general information on the pregnancy and its outcome for all EDP reports with an unknown outcome. The investigator will follow the pregnancy until completion (or until pregnancy termination) and notify Pfizer Safety of the outcome as a follow-up to the initial EDP supplemental form. In the case of a live birth, the structural integrity of the neonate can be assessed at the time of birth. In the event of a termination, the reason(s) for termination should be specified and, if clinically possible, the structural integrity of the terminated fetus should be assessed by gross visual inspection (unless pre-procedure test findings are conclusive for a congenital anomaly and the findings are reported).

If the outcome of the pregnancy meets the criteria for an SAE (ie, ectopic pregnancy, spontaneous abortion, intrauterine fetal demise, neonatal death, or congenital anomaly [in a live-born baby, a terminated fetus, an intrauterine fetal demise, or a neonatal death]), the investigator should follow the procedures for reporting SAEs.

Additional information about pregnancy outcomes that are reported to Pfizer Safety as SAEs follows:

- Spontaneous abortion includes miscarriage and missed abortion;
- Neonatal deaths that occur within 1 month of birth should be reported, without regard to causality, as SAEs. In addition, infant deaths after 1 month should be reported as SAEs when the investigator assesses the infant death as related or possibly related to exposure to the investigational product.

Additional information regarding the EDP may be requested by the sponsor. Further follow-up of birth outcomes will be handled on a case-by-case basis (eg, follow-up on preterm infants to identify developmental delays). In the case of paternal exposure, the investigator will provide the subject with the Pregnant Partner Release of Information Form to deliver to his partner. The investigator must document in the source documents that the subject was given the Pregnant Partner Release of Information Form to provide to his partner.

8.4.3.2. Exposure During Breastfeeding

Scenarios of exposure during breastfeeding must be reported, irrespective of the presence of an associated SAE, to Pfizer Safety within 24 hours of the investigator's awareness, using the CT SAE Report Form. An exposure during breastfeeding report is not created when a Pfizer drug specifically approved for use in breastfeeding women (eg, vitamins) is administered in accord with authorized use. However, if the infant experiences an SAE associated with such a drug's administration, the SAE is reported together with the exposure during breastfeeding.

8.4.3.3. Occupational Exposure

An occupational exposure occurs when, during the performance of job duties, a person (whether a healthcare professional or otherwise) gets in unplanned direct contact with the product, which may or may not lead to the occurrence of an AE.

An occupational exposure is reported to Pfizer Safety within 24 hours of the investigator's awareness, using the CT SAE Report Form, regardless of whether there is an associated SAE. Since the information does not pertain to a subject enrolled in the study, the information is not recorded on a CRF; however, a copy of the completed CT SAE Report Form is maintained in the investigator site file.

8.4.4. Medication Errors

Other exposures to the investigational product under study may occur in clinical trial settings, such as medication errors.

Safety Event	Recorded on the CRF	Reported on the CT SAE Report Form to Pfizer Safety Within 24 Hours of Awareness
Medication errors	All (regardless of whether associated with an AE)	Only if associated with an SAE

8.4.4.1. Medication Errors

Medication errors may result from the administration or consumption of the investigational product by the wrong subject, or at the wrong time, or at the wrong dosage strength.

Medication errors include:

- Medication errors involving subject exposure to the investigational product;
- Potential medication errors or uses outside of what is foreseen in the protocol that do or do not involve the participating subject.

Such medication errors occurring to a study participant are to be captured on the medication error page of the CRF, which is a specific version of the AE page.

In the event of a medication dosing error, the sponsor should be notified immediately.

Whether or not the medication error is accompanied by an AE, as determined by the investigator, the medication error is recorded on the medication error page of the CRF and, if applicable, any associated AE(s), serious and non-serious, are recorded on an AE page of the CRF.

Medication errors should be reported to Pfizer Safety within 24 hours on a CT SAE Report Form **only when associated with an SAE**.

9. DATA ANALYSIS/STATISTICAL METHODS

Detailed methodology for summary and statistical analyses of the data collected in this study is outlined here and further detailed in a statistical analysis plan (SAP), which will be maintained by the sponsor. The SAP may modify what is outlined in the protocol where appropriate; however, any major modifications of the primary endpoint definitions or their analyses will also be reflected in a protocol amendment.

9.1. Sample Size Determination

Although approximately 130 subjects are estimated to be enrolled into this study (based on availability of eligible subjects from the open label Study A3921139 and based on the conservative assumptions of the attrition rate of 50% - 50% in Study A3921139), the final sample size may exceed 130 subjects. The Sponsor will continue to engage with investigative sites participating in Study A3921139 to assess the ability to enroll additional eligible subjects.

With 130 (65 per group) subjects, the estimated half width of the 95% confidence for treatment difference between tofacitinib 10 mg BID and 5 mg BID in proportion of remission at Month 6 based on the modified Mayo score is about 16%, assuming the remission rates are greater than 70% in both groups.

At the time of Amendment 2, 138 subjects have been enrolled and approximately 122 subjects have crossed their Month 6 study visit, the timepoint of the primary endpoint.

9.2. Efficacy Analysis

9.2.1. Analysis Population

The primary analysis population will be the Full Analysis Set (FAS) defined as all subjects who are randomized into the study and receive at least 1 dose of investigational product.

9.2.2. Primary Analysis

The primary endpoint is remission based on the modified Mayo score at Month 6. The primary analysis will be performed at Month 6 based on the FAS for the estimation of treatment difference between the following two dose groups:

- Tofacitinib 10 mg BID Dose Group: subjects who are initially assigned to tofacitinib 10 mg BID at randomization
- Tofacitinib 5 mg BID Dose Group: subjects who are initially assigned to tofacitinib 5 mg BID at randomization, regardless of whether the dose is escalated back to tofacitinib 10 mg BID or not.

The stratified estimation of the treatment difference between tofacitinib 10 mg BID and 5 mg BID in the proportion of subjects with remission at Month 6 will be presented along with its 95% confidence interval (CI). The Cochran-Mantel-Haenszel (CMH) weight method will be used for the stratified estimation of the treatment difference. The stratified CI will be constructed using the NewCombe method. Subjects with dose escalation prior to Month 6 or with missing values at Month 6 will be treated as non-responders at Month 6.

Sensitivity analyses for handling with missing data will be performed. An analysis using a generalized linear mixed-effects model may be performed for the remission endpoint based on data collected at Month 6, Month 12, Month 18, Month 30, and Month 42 if sufficient data are available at Month 42. Further details will be provided in the statistical analysis plan.

9.2.3. Secondary Analysis

Dose comparison between tofacitinib 5 mg BID and 10 mg BID

For the primary objective, the treatment difference for the binary secondary efficacy endpoints will also be estimated based on the FAS, using the same approach as described above for the primary endpoint. For continuous endpoints, the change from baseline will be analyzed using linear mixed-effects model with baseline value, dose group, the endoscopic

subscore at baseline (0 versus 1), visit, and dose group by visit interaction all as fixed effects, and subject as a random effect. The adjusted estimations and associated 95% CI for the overall difference between the two dose groups will be computed. Kaplan-Meier estimates at the scheduled visits will be computed for time to event endpoint. The log-rank test stratified by endoscopic subscore at baseline (0 versus 1) will also be performed for the comparison between dose groups.

If a subject has a dose escalation back to tofacitinib 10 mg BID, then

- For binary efficacy endpoints, the subject will be considered as a non-responder for any visit after the dose escalation visit.
- For continuous efficacy endpoints, the data collected for any visit after the dose escalation visit will be considered as missing.
- For time to loss of remission, the subject will be considered as having an event at the visit with a dose escalation if the event criteria are met or having a censor time at the visit with a dose escalation if the event criteria are not met.

For continuous endpoints that are measured repeatedly over time, the missing values will be handled in a linear mixed-effects model where the *mechanism of missingness* is assumed to be missing at random.

Regimen comparison between flexible dosing and fixed dosing

For the first secondary objective, analyses will be performed based on the FAS for comparisons of the following two dose regimens:

- Tofacitinib fixed 10 mg BID Dose Regimen: subjects who are initially assigned to tofacitinib 10 mg BID at randomization and stay on tofacitinib 10 mg BID until completion or discontinuation.
- Tofacitinib flexible 5 mg/10 mg BID Dose Regimen: subjects who are initially assigned to tofacitinib 5 mg BID at randomization, staying on tofacitinib 5 mg BID or having dose escalation from tofacitinib 5 mg BID to 10 mg BID.

Analysis methods are the same as the ones described above for comparison between dose groups except that data from subjects with dose escalation back to tofacitinib 10 mg BID will be treated as it is. Only the visits with missing data will be treated as non-responders.

For the second secondary objective, summary descriptive statistics will be reported for the sub-group of subjects who are initially assigned to tofacitinib 5 mg BID and later are retreated with tofacitinib 10 mg BID. Missing data will not be imputed.

9.3. Analysis of Biomarker Endpoints

Fecal calprotectin and hs-CRP data and change from baseline will be summarized descriptively by dose group and by dose regimen. Fecal calprotectin and hs-CRP data will also be log-transformed (natural logarithm) for the analyses. The change from baseline will be analyzed using a linear mixed effects model with baseline value, dose group, the endoscopic subscore at baseline (0 versus 1), visit, and dose group by visit interaction all as fixed effects, and subject as a random effect.

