2.2. Study Design

This is a Phase 3b/4, multi center, randomized double blind study. This study will enroll subjects from currently ongoing Study A3921139 who are in stable remission on tofacitinib 10 mg BID for at least 6 months and who are not receiving any corticosteroids to treat their UC for at least 4 weeks prior to enrollment. Subjects must have been receiving tofacitinib 10 mg BID for a minimum of 2 consecutive years in Study A3921139 prior to baseline in order to be eligible for this study. Eligible subjects will be randomized in a 1:1 allocation ratio to receive either tofacitinib 5 mg BID or 10 mg BID at baseline of Study A3921288. Subjects will be stratified at baseline based on the endoscopic subscore (0 versus 1) of their most recent endoscopy.

Although approximately 130 subjects are estimated to be enrolled into this study (based on availability of eligible subjects from Study A3921139 and based on the conservative assumptions of the attrition rate of 50% - 60% in Study A3921139), the final sample size may exceed 130 subjects. The Sponsor will continue to engage with investigative sites participating in Study A3921139 to assess the ability to enroll additional eligible subjects. This study will have a total of 42 months of treatment duration. The primary analysis will be conducted after the last subject enrolled reaches their Month 6 study visit. The study will remain double-blinded to the site and subject to the initial treatment assignment at baseline.

Study visits will occur at baseline (enrollment), and at Months 1, 3, 6, 9, 12, 15, 18, 21, 24, 27, 30, 33, 36, 39 and 42. All subjects, who withdraw early or who complete this study, will have a 4 week safety follow up evaluation after the last dose of investigational product. A schematic of the study design is shown in Figure 1.

Figure 1. Study Design

*All subjects must have an endoscopy performed in Study A3921139 \leq 6 months prior to baseline of Study A3921288 with an endoscopic subscore of 0 or 1, in order to be eligible for enrollment. Local site read of endoscopy only.

During the course of the study, if a subject experiences an increase in clinical symptoms, such as an increase in rectal bleeding or an increase in stool frequency, then an endoscopy should be performed to assess if the subject is experiencing flare. Flare must be confirmed prior to performing any dose adjustments.

Flare is defined by meeting one of the following 4 criteria:

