5.2.2. Analyses for Continuous Efficacy Data

The descriptive statistics will be used to summarize continuous data. The continuous data and change from baseline will be summarized descriptively by visit and dose group, regimen group and the subgroup of subjects who are initially assigned to tofacitinib 5 mg BID and later are retreated with tofacitinib 10 mg BID.

For continuous efficacy endpoints based on total Mayo score evaluated for primary objective at Month 6, the change from baseline will be analyzed using an analysis of covariance (ANCOVA) model with dose group, the endoscopic subscore at baseline (0 versus 1) as factors and baseline score as a covariate. Otherwise, for continuous efficacy endpoints, the change from baseline will be analyzed using linear mixed effects model with baseline value, dose group or regimen group, the endoscopic subscore at baseline (0 versus 1), visit, and dose group or regimen group by visit interaction all as fixed effects, and subject as a random effect. The adjusted estimations and associated 95% CI for the overall difference between the two dose groups or two regimen groups will be computed at each visit.

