5.3.3. Method of Handling the Data after Dose Escalation or Dose Reduction

For this study, subjects may have a dose escalation to 10 mg BID due to flare or dose reduction to 5 mg BID due to PE risk factors. The data after the dose change for the dose group and regimen group are handled as follows.

- For Tofacitinib 10 mg BID dose group: For subjects with dose reduction due to PE risk factor, data collected after the dose reduction will not be included in the safety and efficacy analyses, and last observation carried forward (LOCF) will be used for binary and continuous efficacy endpoints. The subjects will be considered as censored at the dose reduction time for endpoint of time to loss of remission (flare).
- For Tofacitinib 5 mg BID dose group: data collected after the dose escalation (with or without dose reduction due to PE risk factor after the dose escalation) from tofacitinib 5 mg BID to 10 mg BID will not be included in the safety and efficacy analyses. The subjects will be treated as non-responders for any visit after the dose escalation visit for binary efficacy endpoints. For continuous efficacy endpoints, the data collected for any visit after the dose escalation visit will be considered as missing. For time to loss of remission (flare), the subject will be considered as having an event at the visit with a dose escalation if the event criteria are met or having a censored time at the visit with a dose escalation if the event criteria are not met.
- For Tofacitinib 10 mg BID regimen group: For subjects with dose reduction due to PE risk factor, data collected after the dose reduction will be included in the safety and efficacy analyses.

- For Tofacitinib 5 mg BID regimen group: Data collected after the dose escalation will be included in the analyses. For subjects with dose reduction due to PE risk factor after the dose escalation, data collected after the dose reduction will be included in the safety and efficacy analyses.

The following table provides some examples on how to handle the data after the dose escalation for flare and dose reduction for risk factors for PE:

Table 2 Examples on How to Handle Data After Dose Change

Examples	Dose group		Regimen group	
	Safety analysis	Efficacy analysis	Safety analysis	Efficacy analysis

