6.2. Secondary Efficacy Endpoints

Time to loss of remission (flare) based on modified Mayo score will be analyzed as described in [Section 5.2.4](#).

Binary secondary efficacy endpoints will be analyzed using the same approach as described for the primary efficacy endpoint.

Change from baseline (of Study A3921288) in modified Mayo score, modified partial Mayo score, total Mayo score, and partial Mayo score will be analyzed as described in [Section 5.2.2](#).

Fecal calprotectin and hs-CRP, and their change from baseline will be summarized descriptively for each visit by dose group and by regimen group.

The fecal calprotectin and hs-CRP data will also be log-transformed (natural logarithm) for the analyses. The change from baseline will be analyzed using the same approach as the continuous efficacy.

CCI

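### One baseline slope for all visits from Month 1 to Month 42 can bias late visit-specific dose differences in calprotectin and hs-CRP if the baseline relation changes over time and missingness is both unequal by arm and related to baseline

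*Protocol*

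**What the plan says.** Protocol 9.3 models change in the log-transformed biomarkers with a "linear mixed effects model with baseline value, dose group, the endoscopic subscore at baseline (0 versus 1), visit, and dose group by visit interaction". Protocol 9.2.3 lists the same terms for the continuous efficacy endpoints. SAP 5.2.2 also has a single baseline term, and its only interaction is group by visit: "visit, and dose group or regimen group by visit interaction all as fixed effects, and subject as a random effect". SAP 6.2 sends calprotectin and hs-CRP through that model: "The change from baseline will be analyzed using the same approach as the continuous efficacy". Neither document has a baseline-by-visit term.

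Visits are "at Months 1, 3, 6, 9, 12, 15, 18, 21, 24, 27, 30, 33, 36, 39 and 42" (SAP 2.2), 15 after baseline.

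The two documents differ on the contrast. Protocol 9.2.3 says the "overall difference between the two dose groups will be computed". SAP 5.2.2 says the "overall difference between the two dose groups or two regimen groups will be computed at each visit".

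For the 5 mg dose group, SAP 5.3.3 states: "For continuous efficacy endpoints, the data collected for any visit after the dose escalation visit will be considered as missing". Under Protocol 5.11 a 10 mg subject with confirmed flare stays on 10 mg, so that subject's data remain. SAP 5.3.3 fills the later visits of dose-reduced 10 mg subjects by LOCF. In the regimen comparison, post-escalation data are kept.

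**The concern.** A model with one baseline slope assumes that baseline predicts change as strongly at Month 42 as at Month 1. For a fluctuating marker, correlation with a baseline value would be expected to weaken over three and a half years, so the slope of change on baseline would become steeper. Randomization balances baseline at the start. If high-baseline subjects leave the 5 mg data more often, the arms still observed late in the study differ in baseline, and the pooled slope under-corrects that difference. Missing at random (SAP 5.3.1) does not protect the estimate if the mean model is wrong.

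At stake are the late visit-specific differences. One stated reason for extending the study from 18 to 42 months (Amendment 1 rationale) was to see whether efficacy separates between the doses over a longer period. This bias points toward such a separation even when the true difference is zero. At early visits the cost is precision, because chance baseline imbalance is adjusted with the wrong slope.

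**Working it through.** **The plan's own figure.** The documents give no design figure for the repeated-measures model. Their only one is the half-width for Month 6 remission (Protocol 9.1, about 16%). It reproduces: 1.96 × √(2 × 0.70 × 0.30 / 65) = 0.158. It has no bearing on this point.

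**Inputs from the documents.** 138 enrolled, 1:1, so about 69 per arm; 15 visits; one baseline slope; group by visit; subject as a random effect; post-escalation 5 mg data missing.

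**Assumed inputs (not in the documents).** The slope of the visit value on baseline, r, falls linearly from 0.7 at Month 1 to 0.3 at Month 42 (mild: 0.6 to 0.45; steep: 0.8 to 0.1). At Month 42, 46–49% of 5 mg and 77–81% of 10 mg subjects are still observed. The log-odds of going missing rise by 0, 0.3 or 0.7 per baseline SD, or by 0.7 per SD of the last observed value. The true dose difference is zero.

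**Approximation.** The slope of change on baseline at visit t is β(t) = r(t) − 1. With pooled slope β̄, and Δb(t) the 5 mg minus 10 mg difference in mean baseline among subjects still observed:

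bias(t) ≈ [β(t) − β̄] × Δb(t)

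Example (log-odds 0.7): (−0.70 + 0.44) × (−0.272) = +0.071.

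**Month 42 results in baseline SD, 40,000 per arm** (simulation standard error about 0.006 to 0.008)

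| Scenario | β(42) | β̄ | Δb | Product | Planned model | With interaction |
|---|---|---|---|---|---|---|
| Constant slope; unequal, baseline-related loss | −0.40 | −0.40 | −0.272 | 0.000 | −0.004 | −0.006 |
| Changing slope; nothing missing | −0.70 | −0.50 | −0.001 | 0.000 | +0.001 | +0.001 |
| Changing slope; unequal loss unrelated to baseline | −0.70 | −0.46 | +0.011 | −0.003 | +0.011 | +0.014 |
| Changing slope; baseline-related loss, equal rates (47–48% observed) | −0.70 | −0.42 | +0.003 | −0.001 | +0.007 | +0.008 |
| All three conditions, log-odds 0.3 | −0.70 | −0.46 | −0.141 | +0.034 | +0.036 | −0.005 |
| All three, log-odds 0.7 | −0.70 | −0.44 | −0.272 | +0.071 | +0.094 | +0.011 |
| All three, 0.7, mild slope change | −0.55 | −0.46 | −0.274 | +0.025 | +0.039 | +0.008 |
| All three, 0.7, steep slope change | −0.90 | −0.45 | −0.269 | +0.121 | +0.142 | −0.002 |
| Loss driven by last value | −0.70 | −0.46 | −0.161 | +0.039 | +0.061 | +0.011 |

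The first four rows each remove one condition, and no bias remains beyond simulation error. Month 1 bias is at most about 0.01 throughout.

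**At trial size** (69 per arm, 1,000 replicates, planned model), bias over standard error at Month 42:
- mild slope change: 0.031 / 0.182 = 0.17
- log-odds 0.3: 0.056 / 0.182 = 0.31
- log-odds 0.7: 0.084 / 0.183 = 0.46
- last value: 0.052 / 0.187 = 0.28
- steep slope change: 0.135 / 0.188 = 0.72

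With the interaction, bias is between −0.006 and +0.013.

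**A second data structure.** Here correlation decays with time as 0.2 + 0.6 exp(−t/12), the log-scale SD is 1.2, there are 70 per arm, and loss depends on the current value. A random subject intercept is fitted. Month 42 bias falls from +0.037 to −0.001 (0.037 / 1.2 = 0.03 SD). With steeper decay it falls from +0.116 to +0.036 (0.116 / 1.2 = 0.10 SD). RMSE falls from 0.153 to 0.136 at Month 1 and from 0.280 to 0.270 at Month 42. Coverage does not improve: 91.4% against 91.1%.

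**Scale.** With a log SD of 1, 0.03 to 0.14 SD is a ratio of exp(0.03) = 1.03 to exp(0.14) = 1.15. For partial Mayo, entry is limited to scores of 0 to 2 (Protocol 4.1), so the baseline SD is at most about 1 point and the bias at most about 0.14 point.

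**The case against.** The strongest reply is that only one of the three conditions comes from the plan. The post-escalation rule supplies unequal loss. A changing slope and baseline-related loss are plausible, but the documents give no figure for either. Flare is defined by rectal bleeding, stool frequency and endoscopic subscores (Protocol 5.11), not by calprotectin or hs-CRP, so for the biomarkers the link from baseline to loss is indirect. This stands, and it is why the point is conditional.

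A reader might infer that the excess of missing 5 mg data biases the late differences by itself. The third row of the table shows that it does not.

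A reader might also expect the extra term to bring intervals back to 95%. It does so in simulations where the fitted covariance matches the data: 90.8% to 95.0% in the log-odds 0.7 scenario. With decaying correlation and a random intercept there was no gain. That shortfall is a covariance matter, so no coverage benefit should be claimed.

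Scope is narrow. SAP 5.1 tests no formal hypotheses, these are secondary endpoints, and observed-data summaries are also planned. The visit-specific contrast comes from the SAP only; for the Protocol's overall difference the bias in the log-odds 0.7 scenario is +0.037 SD. LOCF for dose-reduced 10 mg subjects was not simulated. These points limit the weight of the concern but do not remove the reason for a one-term correction.

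**Conclusion.** The concern holds in conditional form. In the dose-group comparison, the single baseline slope can bias late visit-specific differences, mainly for log calprotectin and log hs-CRP, when all three conditions hold. The Month 42 bias is about 0.03 to 0.14 baseline SD, roughly 0.15 to 0.7 standard errors, against 5 mg. Early-visit estimates are also less precise than they could be. All sizes rest on assumed slopes, dropout rates and dropout mechanisms.

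The Month 6 primary remission analysis and the Month 6 total Mayo ANCOVA are not touched. The regimen comparison lacks the escalation-driven imbalance. Partial Mayo was not simulated directly; its bound of about 0.14 point does not support treating it as a material problem. This is a cheap improvement to secondary analyses, not a threat to the trial's main result.

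**What to change.** In Protocol 9.2.3 and 9.3 and SAP 5.2.2, add a baseline-by-visit interaction to the fixed effects of the repeated-measures models, using log baseline for the two biomarkers. Estimate the visit-specific differences at the overall mean baseline. State whether the overall or the visit-specific difference is the target, since Protocol and SAP differ. SAP 7.1 has the sponsor's study team unblinded from the Month 6 analysis, so date and justify the change before the final analysis.

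The cost is up to 14 degrees of freedom (15 slopes in place of one) and about 1% in the Month 42 standard error (0.266 to 0.268 when the generating covariance is fitted; no rise with a random intercept). No new data are needed. Describe the benefit as less bias and lower RMSE only.
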